10.3. Safety Outcomes

Participants will be assessed/asked at each visit, specifically about safety outcomes.

The following are specific intraoperative and postoperative complications of cataract surgery and will be recorded and reported on the study worksheets:

- Zonulodyalisis
- Iridodyalisis
- Posterior capsule rupture
- Posterior dislocated lens fragments
- Anterior and posterior synechiae (in clock hours)
- Optic capture and whether or not this resulted in subsequent problems
- Posterior capsule opacification
- Opacification of the intraocular lens

It will be recorded whether or not these previously listed complications are associated with patient's symptoms (e.g. photophobia) upon questioning the participant, and/or whether or not they lead to inability/difficulty to visualise the fundus by the investigator as a result. Other possible complications of cataract surgery (not listed above) will be captured in the CORDs complication list below (e.g. non-infectious uveitis, endophthalmitis).

In addition, safety outcomes related to the vitrectomy, will be recorded and reported following the CORDS classification below (18,19). Minor complications (scored 1 or 2) will not need to be reported.

Complication	Median
General intraoperative	area an
Subconjunctival hemorrhage	1
Chemosis	1
Subretinal hemorrhage not involving macula, ≤1 quadrant	3
Subretinal hemorrhage not involving macula, >1 quadrant	4
Suprachoroidal hemorrhage not involving macula and no kissing*	5
Subretinal hemorrhage involving macula, ≤3 disc areas	7
Subretinal hemorrhage involving macula, >3 disc areas	8
Suprachoroidal hemorrhage involving macula or kissing	9
General postoperative	
Subconjunctival hemorrhage	1
Chemosis	1
Refractive changes: <2-dimensional	2
Early raised IOP, self-resolving	2
Early hypotony, self-resolving	2
Serous choroidal detachment: peripheral	3
Persistent localized subretinal fluid: peripheral, nonprogressive	3
Visual field loss not related to retinal detachment but attributable	4
to surgical procedure: not affecting driving license	
Refractive changes: ≥2-dimensional	4
Persistently raised IOP manageable with drops	4
IOL displacement	4
Macular edema	4
Suprachoroidal hemorrhage: not involving macula and no kissing	5
Persistent localized subretinal fluid: submacular	5
Loss of visual acuity attributable to surgical procedure: moderate (3-5 lines ETDRS chart)	6
Persistent hypotony (IOP <5 mm Hg) without macular folds	6
IOL dislocation	6
Macular hole formation	6

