10.2. Secondary Outcome Measures

All at 52 weeks (+/- 6 weeks) after surgery for all outcomes except *:

- Primary anatomical success (proportion of eyes with an attached retina after one vitrectomy).
- Final anatomical success (proportion of eyes with an attached retina after two or more vitrectomies).
- Intraoperative complications (total number and by severity score). (18, 19).
- Postoperative complications (total number and by severity score). (18,19).
- Number and type of surgeries performed.
- Refractive error* (difference between aimed (sought) and obtained post-operative refraction
 12 weeks after surgery in the phaco-vitrectomy arm and 6-8 weeks post-cataract surgery, if this takes place, as per standard of care, in the vitrectomy only arm).
- Proportion of participants with BCVA <69 letters
- Proportion of participants with BCVA <34 letters.
- Time to achieve 'best vision'.
- Change in BCVA from baseline over time.
- Health related quality of life measured using EuroQol-5 level (EQ-5D-5L) (20).
- Vision-specific quality of life measured using the National Eye Institute Visual Function Questionnaire-25 (NEI VFQ-25) (21).
- Participant's experience, and acceptability of treatments.
- Use of health and social care services and non-health care costs.
- Safety

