15.2. Adverse Eventing Recording and Reporting

The AE reporting period for the trial begins upon consent and ends at week 52 (the last follow up visit). All reportable unexpected AEs/ARs and SAEs/SARs should be followed until they are resolved. If the event has not been resolved by the time of the participant's 52-week visit, it will be recorded as ongoing.

The PI or designee should record all directly observed AEs/ARs and those spontaneously reported by the participant in trial worksheets (which constitute the data source for the trial), which will then be filed or uploaded in the medical records of the participant, in accordance with GCP.

It is expected that many participants will experience events that are in keeping with pre-existing medical conditions rather than being related to the trial. Events associated with any pre-existing medical conditions that the participant may have when entering the trial will not need to be reported. The exception to this will be death: even if death occurs as a result of the participant's pre-existing condition, death should be reported as a SAE.

Refractive error will be studied in detail as an outcome of the trial. Thus, this will not be reported as an AE. All other, general or specific complications of pars plana vitrectomy, will be reported.

Potential visual field loss will be investigated and confirmed by obtaining a visual field in patients complaining of loss of peripheral vision at any point during the trial. If confirmed, visual field loss will be recorded in the corresponding worksheet.

Treatments used for complications occurring in CORDS will be recorded. If as a result of the occurrence of a complication a participant needs to be admitted to the hospital for treatment, this will be reported as a SAE/SAR.

Development/progression of a cataract in the vitrectomy group will be recorded and reported. Cataracts will be graded following the AREDS classification (16). Development of cataract will be determined when there is progression from no cataract (i.e. Nuclear Sclerosis [NS] and Posterior Subcapsular [PSC] and Cortical Sclerosis [CS] \leq 1) to any cataract (i.e. NS and/or PSC and/or CS >1). Progression of cataract will be considered when there is progression from any cataract to higher stages (i.e. from 1 to any higher grade: 2 or 3) (16).

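### Sections 10.3, 12.4 and 15.2 disagree on whether CORDS complications scored 1 or 2 are collected and counted, so the secondary outcome of total complications has no single definition; the place of the refractive items in it is also unclear

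*Protocol*

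**What the plan says.** Four sections of the protocol bear on what is collected and counted.

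- **Section 10.2** lists intraoperative complications and, in the same form, "Postoperative complications (total number and by severity score", as secondary outcomes at 52 weeks. It states no minimum score. It also lists refractive error as a separate outcome, defined as aimed against obtained refraction.
- **Section 10.3** says that "safety outcomes related to the vitrectomy, will be recorded and reported following the CORDS classification below" and then exempts the lowest grades: "Minor complications (scored 1 or 2) will not need to be reported". The printed list includes "Refractive changes: <2-dimensional" at score 2 and "Refractive changes: ≥2-dimensional" at score 4, without naming the refraction from which change is measured. The same section lists eight complications of cataract surgery that carry no CORDS score.
- **Section 12.4** says complications are recorded prospectively with CORDS, scored and analysed, and that cataract-surgery complications are recorded too. It makes no exception for low scores.
- **Section 15.2** says: "Refractive error will be studied in detail as an outcome of the trial. Thus, this will not be reported as an AE". The next sentence reads: "All other, general or specific complications of pars plana vitrectomy, will be reported".

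**The concern.** A count outcome is only as well defined as the list of events that may enter it. Here one section exempts scores 1 and 2, two others do not, and the outcome definition does not say which rule governs. The wording in 10.3 is also permissive: it says that minor events need not be reported, not that they are to be left out. One site could enter them while another omits them.

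Section 9.4 masks the optometrists who measure the primary outcome, but not the staff who deliver treatment, and section 7.1 plans at least 30 sites. Uneven entry could therefore shift the total by site or by arm without any difference in harm. A later analysis plan could restrict the count to higher scores, but it cannot recover minor events that were never collected. The collection rule has to be settled in the protocol.

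The refractive items raise a second question. Every phacovitrectomy eye receives an intraocular lens (section 8.1), and a lens may change refraction by plan. If change is measured from baseline, a planned result could be counted as a score 4 complication.

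**Working it through.** The plan states no figure on this point, so the check is a count of the printed list followed by a comparison of the rules.

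**Count of CORDS items in section 10.3 by printed score.** The last two blocks appear without headings in the text available; their items were assigned to intraoperative or postoperative by content.

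| Block | Items | Scored 1 or 2 |
|---|---|---|
| General intraoperative | 8 | 2 |
| Second intraoperative block | 10 | 3 |
| General postoperative | 29 | 5 |
| Second postoperative block | 15 | 0 |

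Intraoperative: 8 + 10 = 18 items, of which 2 + 3 = 5 are minor. Postoperative: 29 + 15 = 44 items, of which 5 + 0 = 5 are minor. Together: 18 + 44 = 62 items, 10 of them minor. The minor items include subconjunctival haemorrhage, chemosis and self-resolving pressure changes.

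**Items that can enter the total under each reading.**

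| Rule followed | Intraoperative | Postoperative | Total |
|---|---|---|---|
| 12.4: all items | 18 | 44 | 62 |
| 15.2 taken literally, both refractive items dropped | 18 | 44 − 2 = 42 | 60 |
| 10.3: scores 1 and 2 exempt | 18 − 5 = 13 | 44 − 5 = 39 | 52 |
| 10.3 plus the refractive exemption in 15.2 | 13 | 39 − 1 = 38 | 51 |

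In the last row only one further item goes, because the lower refractive item already falls under the score 1 or 2 exemption. These are numbers of eligible item types, not of expected events. The documents give no complication rates, so the effect on the count per arm cannot be worked out.

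**Refractive items: two readings.**

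1. *Aimed against obtained refraction*, as 10.2 defines refractive error. A planned change then scores nothing. However, the list in 10.3 would count a deviation that 15.2 sets aside, and the same deviation would feed two secondary outcomes.
2. *Change from baseline.* A planned change from an implanted lens could then be counted. The exemption in 15.2 names refractive error, so it does not clearly reach this quantity.

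The protocol does not choose between them. The unit printed beside the refractive threshold is not relied on here.

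**The case against.** The strongest defence is that 10.3 is the specific rule for CORDS items and 15.2 concerns adverse event reporting, with its mention of general or specific complications pointing back to the list and its exemption. The trials unit supplies the same worksheets and eCRF to all sites (section 13.1), which limits local discretion. The outcome is also reported by severity score, so higher grades can be separated from any minor events entered.

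Part of this stands: a coherent reading exists, and differential entry by arm is a risk, not something shown. But the protocol does not state that reading, and section 15.6 weakens it. Complications listed in 10.3 count as expected, and only unexpected events and serious events go on the AE and SAE forms. For a non-serious listed complication, the duty in 15.2 is then most naturally read as the worksheet reporting that 10.3 governs. Reporting by severity also leaves the overall total undefined.

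A reader might go further and infer that 10.3 and 15.2 flatly contradict each other on refractive change, and that the protocol counts intended change as harm. The documents do not support this. Those two claims need different reference refractions, and no section says that a planned result is a complication. The sentence "Thus, this will not be reported as an AE" can itself be read as setting the matter apart.

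Nor can the effect be sized or assigned to one arm. The protocol gives no distribution of baseline or aimed refraction. Comparator eyes also receive lenses when cataract develops: section 4.1 reports that 320 of 664 such eyes (48%) had a cataract recorded or already removed within three months, and that only 20% had a clear natural lens at 12 months. How many will have had cataract surgery by week 52 is not given.

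**Conclusion.** The point holds for minor complications. Sections 10.3, 12.4 and 15.2 give incompatible rules for 10 of 62 listed items, and section 10.2 counts the total with no threshold. Two secondary outcomes are affected; the primary outcome is not. The proportion of item types in dispute is larger for the intraoperative total (5/18 = 28%) than for the postoperative one (5/44 = 11%). What this does to event counts is unknown. The concern about bias rests on the permissive wording and on unmasked entry across many sites, not on any evidence of uneven recording.

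On refractive change the finding is an ambiguity: the protocol does not say whether the items count or against which refraction. Counting planned change as a complication is possible only if the reference is baseline. The text should be settled before the outcome is collected and analysed.

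**What to change.** Reconcile sections 10.2, 10.3, 12.4 and 15.2 so that they state one rule:

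1. The total counts CORDS complications scored 3 or more, identically in both arms. Events scored 1 or 2 are excluded from the total even if a site enters them.
2. The eight unscored cataract-surgery complications in 10.3 are kept, either as a named component of the total or as a separate count. A bare threshold of 3 would otherwise drop them all, including posterior capsule rupture and dislocated lens fragments, although they are possible harms of the procedure added in the intervention arm.
3. Planned refractive change after lens implantation is not counted as a complication. Nor is the aimed-against-obtained deviation, which is already analysed as refractive error.
4. Unplanned refractive change in eyes without cataract surgery remains captured, with its reference refraction stated. Removing the refractive items outright would lose it, because refractive error in the vitrectomy arm is measured only after cataract surgery.
5. Section 15.2 is reworded to match.

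The cost is wording in four sections, with no change to treatment or visits. The downside is that minor events drop out of the count. Requiring every site to record all scores would also remove the conflict and keep those events, at the price of more data collection.

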10.4. Definition of Study Eye

The unit of randomisation will be the participant, not the eye. In participants presenting with RRD in both eyes, if both eyes are eligible, the "study eye" will be the eye with the best BCVA. If both eyes have the same BCVA, the study eye will be, arbitrarily, the right eye. If both eyes are eligible, the fellow eye would be treated, if possible, in the same way as the study eye. For instance, if both eyes of a patient are eligible and the randomisation allocates vitrectomy for the study eye, the fellow eye would receive vitrectomy too, if possible. This would apply also if the fellow eye does not have a RRD at presentation but develops it during the trial period (i.e. the participant will be offered the same type of surgery in the fellow eye to that received in the Study Eye, provided that this is pertinent and the participant is agreeable).

11. SCREENING, CONSENT and RECRUITMENT

11.1. Recruitment Strategy

COMBAT will include at least 30 sites across the UK. Large and small units across the four nations have been invited to take part in COMBAT to ensure full recruitment and applicability of the results to general practice across the UK. Considering that urgent vitreoretinal cases and specifically RRD are

currently done by vitreoretinal fellows in the UK, vitreoretinal fellows will be allowed to take part in the trial.

Potentially eligible participants will be identified by members of the direct care team from urgent optometry referrals, from Eye Casualty and from Retina and Vitreoretinal clinics at participating sites. A member of the COMBAT team will then meet with potential participants who express interest in taking part in COMBAT in order to give verbal and written details about the trial, including the Participant Information Leaflet (PIL). An audio version of the PIL will be made available where required. If a participant is eligible and provides informed consent, they will be enrolled in the trial. As part of the consent process, patients will be asked if they agree to be invited, at a later date, to take part in a series of 3 (maximum) interviews. Participants will also be asked if, following completion of their participation in the COMBAT trial, data collected as part of their standard care, can be used for future follow-up research.

11.2. Screening Procedure

Participants will be screened against the eligibility criteria specified in this protocol. All screening data will be recorded via electronic data capture (EDC) which must be completed by the Principal Investigator (PI) or designee to document all participants screened for the study and all participants recruited. Participants screened and not recruited to the study will be documented via EDC, including reasons for not being enrolled. A minimal dataset will be recorded for these non-recruited patients which will include Age, Sex at Birth, Sexual Orientation, Ethnicity, Preferred language, Socioeconomic Status (e.g. Employment Status, Education level) and partial post code (with the exception of those in Scotland) to determine if there are differences with those willing to participate and recruited. Consent will not be requested to collect this full minimal dataset as data is fully anonymised and is partially collected as part of standard care. Where these data are not routinely collected, participants will be provided with a brief questionnaire and consent will be implied by its completion and return

The PI or designee will be required to submit screening data to the NICTU at set time points.

11.3. Informed Consent Procedure

The study will be conducted in accordance with the ethical principles that have their origin in the Declaration of Helsinki. Eligible participants may only be included in the trial after written informed consent is obtained. Informed consent must be obtained prior to conducting any trial specific interventions.

A COMBAT PIL will be co-produced by the COMBAT PPI Group and research team. This will contain brief and clear information, in plain English, about the purpose of COMBAT and what will happen if the person wishes to take part in the trial. The NICTU will provide COMBAT PILs approved by the REC, to all sites. The PI or designee will be responsible for ensuring that all participants are given a copy of the PIL and allowed adequate time to review it and the opportunity to ask any study related questions. All participants should have the capacity to self-consent. This should be judged by the PI or the designated member of the study team who will have the responsibility for taking consent. An audio version of the PIL and PILs in languages other than English will be available so that, even if potential participants prefer an audio version or do not understand English, they will be able to read about COMBAT and to join the study, if they wish. This will be highlighted to all sites to support diversity of recruitment.

Informed Consent Forms (ICF) approved by the REC will be provided to all sites by the NICTU. The PI or designee is responsible for ensuring that the ICF is signed and personally dated by the participant before any trial interventions are administered. If consent is not given, a patient cannot be recruited into the trial.

Two copies of the ICF must be signed and personally dated by the participant and the individual taking consent. The signed ICF will either be uploaded to the electronic case records (if the site uses electronic patient records) or filed in the patient's medical notes (if the site uses paper medical records). One signed ICF will be retained by the participant and the other will be kept by the site in the Investigator Site File (ISF).

Following recruitment of a patient, the PI or designee will issue a letter to the participant's General Practitioner (GP) to inform them that their patient is participating in the study, if this is approved by the participant.

11.4. Withdrawal of Consent

Participants may withdraw their consent from the trial at any time without prejudice. If consent is withdrawn, this will be documented in the participant's medical notes and in the CRF. In the event of a request to withdraw from the study, anonymised data recorded up to the point of withdrawal will be included in the study analysis.

COMBAT participants taking part in interviews will be informed that withdrawal of their interview data will not be possible once the interviews have been transcribed.

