12.4. Clinical Outcomes

Best-Corrected Visual Acuity (BCVA)

The primary outcome is change in BCVA from baseline to 52 weeks (+/- 6 weeks) after surgery in the study eye. There is no consensus on the core outcomes to be measured in trials for RRD but BCVA is routinely measured in the standard care of patients with RRD and in ophthalmology trials. It is considered, together with retinal reattachment, as a main outcome of surgical success in clinical practice. BCVA closely relates to patient-reported quality of life. Full-refracted distance BCVA will be measured in both eyes using the ETDRS Visual Acuity charts at 4 meters by masked optometrists/ophthalmologists at baseline and at week 6, 12 and 52 after surgery, following the COMBAT SOP.

Note: If the surgery takes place more than three days after the baseline assessment, or if the patient reports a change in their vision since the baseline assessment, the BCVA should be repeated before the surgery.

Retinal Reattachment

Patients will be evaluated using slit-lamp biomicroscopy with wide angle non-contact or contact lenses and/or indirect ophthalmoscopy, as per standard practice at participating sites, and the status of the retina (fully attached/detached) will be recorded in the appropriate CRF.

Intraoperative and Postoperative Complications

Intra- and post-operative complications will be prospectively recorded using CORDS (The Classification for the Reporting of Complications in Retinal Detachment Surgical Trials) (19), a robustly developed classification of complications of vitreoretinal surgery (18). Complications will be scored as per this classification and analysed. Intraoperative and postoperative complications of cataract surgery will be also recorded.

Furthermore, presence/absence of posterior capsule opacification (PCO) and performance of YAG laser posterior capsulotomy will be prospectively recorded during the trial in the appropriate CRF (Note: surgeons who routinely do posterior capsulectomy at the time of the phacovitrectomy will be allowed to do so in COMBAT, recording this procedure in the pertinent surgical CRF).

Number and Type of Surgeries Performed

The number and type (e.g. surgery for retinal re-detachment – i.e. if surgical failure occurs; cataract surgery; other) of surgeries performed throughout the trial will be recorded in the appropriate CRFs.

Refractive Error

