Rates of PCO and of YAG posterior capsulotomy will be analysed as per categorical outcomes by using GLM with adjustment for minimisation covariates. Relative risk, risk difference and odds ratio will be reported, where possible. We will undertake a sensitivity analysis on the basis of the performance (or not) of an intraoperative capsulectomy, if numbers allow, to explore the potential effect on outcomes of this manoeuvre. Participants will be consented for COMBAT researchers to review their medical records and establish contact with their optometrist to gather information about whether participants in the vitrectomy only arm receive cataract surgery and, if they do, whether YAG-

capsulotomy is undertaken after the trial ended. These data will be used to provide long-term outcomes with regard to cataract surgery, refractive error, and rates of YAG-posterior capsulotomy.

Missing Data

Every effort will be made to minimise missing baseline and outcome data and data queries will be generated for site staff as required to request missing information.

Standard approaches will be used to detect patterns in missing data. The level and pattern of the missing data in the baseline variables and outcomes will be established by forming appropriate tables and the likely causes of any missing data will be investigated. This information will be used to determine whether the level and type of missing data has the potential to introduce bias into the analysis results for the proposed statistical methods, or substantially reduce the precision of estimates related to treatment effects. We plan for the principal analysis to be based upon available case data with no imputation of missing values. Sensitivity analyses will be undertaken to assess the impact of missing data by imputing extreme values (lowest and highest), as stated above.

A detailed Statistical Analysis Plan (SAP) will be prepared and made publicly available before undertaking the final analysis.

Analysis of Quality of Life Data

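### Section 11.4 has one level of withdrawal, and no routine-record follow-up to week 52 is planned for participants in either arm who stop attending

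*Protocol*

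**What the plan says.** Protocol section 11.4 states: "Participants may withdraw their consent from the trial at any time without prejudice". It continues: "In the event of a request to withdraw from the study, anonymised data recorded up to the point of withdrawal will be included" in the analysis. No intermediate option is described, and the section does not say whether any data may be collected afterwards.

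Section 14.2 (Statistical Methods) provides for another data source: "Participants will be consented for COMBAT researchers to review their medical records and establish contact with their optometrist to gather information". The purpose given is to learn "whether participants in the vitrectomy only arm receive cataract surgery" and, if so, whether YAG capsulotomy follows after the trial. The use is then fixed: "These data will be used to provide long-term outcomes with regard to cataract surgery, refractive error, and rates of YAG-posterior capsulotomy".

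Section 14.2 (Missing Data) says: "We plan for the principal analysis to be based upon available case data with no imputation of missing values". Sensitivity analyses that impute the lowest and highest values are to follow.

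Section 12.4 defines the main endpoint: "The primary outcome is change in BCVA from baseline to 52 weeks (+/- 6 weeks) after surgery in the study eye". It is a fully refracted ETDRS measurement by a masked assessor under a trial SOP. The same section notes that "BCVA is routinely measured in the standard care of patients with RRD".

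**The concern.** People leave trials in different ways. Some want no more visits or questionnaires but do not mind their notes being read; a few want nothing further recorded; others simply stop coming and never withdraw. Section 11.4 has one category for the first two, and no section says how the third group's routine records will be used up to week 52.

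Several secondary outcomes in section 10.2 would normally be found in hospital notes: whether the retina is attached, how many operations the study eye has had, and which complications occurred. If nobody looks, these are missing for anyone who leaves early, and the principal analysis proceeds without them.

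The loss may be selective. Participants know their allocation (section 9.4). Section 4.1 reports that 48% of phakic eyes not given combined surgery had cataract recorded or removed within three months, and that only 20% had a clear natural lens at 12 months. Comparator participants thus have an arm-specific reason to remain under hospital care, so unequal attendance at week 52 is plausible. The protocol does not show that it will happen.

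**Working it through.** **1. The plan's own sample size.** Inputs from section 14.1: SD 15.2 letters, margin 7 letters, two one-sided tests at 2.5%, power 90%, dropout 10%. A true difference of 0 is assumed; it is not stated, but it reproduces the figure.

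- Normal approximation per arm: 2 × 15.2² × (1.960 + 1.645)² / 7² ≈ 122.5, so 123 per arm or 246 in total.
- Exact t-based power for two one-sided tests: 89.8% with 246 and 90.1% with 248. The stated 248 is the exact answer.
- Dropout: 248 / 0.90 = 275.6, so 276.

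Both figures reproduce.

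**2. What the 10% means.** 276 − 248 = 28 participants, about 14 per arm, for losses of every kind. The protocol gives no separate rate for withdrawal of consent. Losing all 28 leaves power at 90.1%; losing none would give 93.6%. Power is therefore covered, and the remaining question is bias.

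**3. Binary outcomes (attachment, re-operation).** With a fraction m missing in each arm, the full-sample difference is

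(1 − m) × observed difference + m × (difference among the missing).

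The last bracket lies between −1 and +1, so the bound is ± m around the first term.

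- m = 10%: 0.9 × observed difference ± 10 points.
- If look-up recovers 70% to 90% of the missing (assumption; the documents give no rate), m falls to 10% × 0.30 = 3% or 10% × 0.10 = 1%, and the bound to ± 3 or ± 1 points.

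For scale, section 4.2 regards a 10% difference in single-surgery success as seemingly clinically important.

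**4. Why ±10 is an extreme.** It needs every missing participant in one arm to fail and every one in the other to succeed. It also treats their status as wholly unknown, whereas Table 2 schedules a fundus examination at weeks 1, 6 and 12 and section 11.4 keeps data already recorded. A failure of the first vitrectomy seen before someone leaves already settles primary anatomical success.

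**5. Primary outcome, for illustration.** If 10% are missing in one arm and their change in BCVA differs from that of the observed participants by 10 to 20 letters (assumption), that arm's mean moves by 0.10 × 10 = 1.0 to 0.10 × 20 = 2.0 letters, against a margin of 7. Record review does not remove this shift, because it cannot supply the masked refracted measurement.

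**6. The provisions side by side.**

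| Group | Covered by | Routine-record follow-up to week 52 |
|---|---|---|
| Asks to stop visits only | Section 11.4, single level | Not described |
| Refuses all further data | Section 11.4, single level | None, properly |
| Stops attending without withdrawing | Section 8.3, general retention effort | Not described |
| Vitrectomy-only arm, cataract and YAG information | Section 14.2 consent | Described, as long-term outcomes |

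**The case against.** The case against is substantial, and much of it stands.

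- A reader might infer from section 11.4 that a request to withdraw ends all data collection. The section states only what happens to data already recorded. That collection stops is the natural reading, but it is an inference.
- A reader might take the 10% as the loss caused by this rule. It is the all-cause allowance already built into 276, and no withdrawal rate is given.
- A reader might suppose that week-52 results can be retrieved from records. For the primary outcome they cannot: routine acuity is neither masked nor taken under the trial SOP.
- A reader might suppose that the section 14.2 consent can be used as it stands. Its stated purpose is narrower, and withdrawing from the trial may withdraw it too.
- Section 12.4 records surgeries throughout the trial without tying this to a visit, and section 8.3 asks teams to retain everyone. Both help, but neither names routine records as a source for people who have stopped attending.
- The extreme-value sensitivity analysis already examines the worst case. It displays the uncertainty, however, and does not reduce it.
- If comparator participants stay under the hospital for cataract and others do not, records near week 52 may be fuller in one arm. Recovery could then itself be unequal. This is a real limit of the remedy.
- The consent form is not in the reviewed text and may already offer levels of withdrawal. Section 11.4 would still need to agree with it.

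**Conclusion.** The point holds as a low-cost improvement to follow-up. Section 11.4 describes one level of withdrawal, and the planned record review does not extend to week-52 outcomes in both arms. Later retinal status, operations and complications are therefore left out for people who stop visits or are lost.

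The size is uncertain. The number affected is unknown. The ±10 points is a worst-case bound at the full 10% missing in each arm, and its reduction to ±1 to 3 points rests on an assumed 70% to 90% recovery. Power for the primary outcome is not at issue. Selective loss by arm is plausible but not demonstrated.

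An analysis plan cannot settle this later, because it cannot use data that nobody was permitted to collect. The levels of consent and the data sources have to be set before enrolment.

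**What to change.** In section 11.4, and in the consent form if it does not already do so, offer two levels of withdrawal:

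- (a) no further trial visits or questionnaires, with record review continuing to week 52;
- (b) no further data of any kind.

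Extend the wording of the record and optometrist consent in section 14.2 to cover this purpose in both arms.

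For level (a), and for participants lost to follow-up without withdrawing, extract retinal status, all operations on the study eye, complications and death. Use these in the anatomical, surgery-count and safety outcomes. Use any routine acuity from weeks 46 to 58 (52 ± 6) only in a sensitivity analysis of the primary outcome, flagged as unmasked. Report the recovery rate by arm, since availability of records may differ.

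Cost: wording in the protocol and consent form, and record extraction for about 28 participants if dropout reaches the planned allowance, fewer if some choose level (b).
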